14.3.1 Disease Activity Endpoints

The following secondary endpoints to be analyzed on mITT analysis set are summarized in [Table 19](#). LLDAS is defined in [Appendix 18.1.7](#).

For SRI-4 and SRI-6 response endpoints as well as LDA status and LLDAS, the primary analysis method applied to the two-primary endpoints ([Section 14.1.2.1](#)) will be performed.

In addition, for LDA and LLDAS endpoints in [Table 19](#), the number and percentage of subjects with response or non-response will be summarized over time (by visit), using similar imputation rules as applied for the Week 52 timepoint.

Table 19 : Disease Activity Endpoints

Endpoint	Analysis method	Data Handling Notes

 • SRI-6 response at Week 52, in the serologically active subgroup • SRI-4 Response at Week 52 with a Sustained Reduction of OCS Dose to 7.5 milligrams prednisone-equivalent per day or less (≤ 7.5 mg/day) and less than or equal to (\leq) Day 1 dose during Week 41 Through Week 52, in all subjects • SRI-6 Response at Week 52 with a Sustained Reduction of OCS Dose to 7.5 milligrams prednisone equivalent per day or less (≤ 7.5 mg/day) and less than or equal to (\leq) Day 1 dose during Week 41 Through Week 52, in the HDA subgroup • SRI-4 Response at Week 52 with a Sustained Reduction of OCS Dose to 7.5 milligrams prednisone equivalent per day or less (≤ 7.5 mg/day) and less than or equal to (\leq) Day 1 dose during Week 41 Through Week 52, in the serologically active subgroup 	Same as the Primary Method in Table 17	Same as the Primary Method in Table 17

 • LDA status, defined by SLEDAI-2K ≤ 2 at Week 52 • LDA, defined by clinical SLEDAI-2K (SLEDAI-2K excluding anti-dsDNA and low complement parameters) ≤ 2 at Week 52 • LLDAS at Week 52 	Same as the Primary Method in Table 17	Same as the Primary Method in Table 17

In order to determine whether the subject had a sustained reduction of OCS Dose to ≤ 7.5 mg/day and \leq Day 1 dose during Week 41 Through Week 52, the daily dose of CS will be calculated for each analysis visit from Week 41 to Week 52, according to Appendix 18.8. If the condition is met for all days during this period, the subject will be considered as having a sustained reduction of OCS Dose.

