14.3.5 Corticosteroid usage over time

CS usage over time will be analyzed on the mITT set using data collected in “Relevant Previous Medications Details” and “Concomitant Medications” eCRF Forms.

Only CS taken at baseline or after will be taken into account. Any CS with an end date before screening date will not be taken into account in the following analysis.

General rules, missing data handling, conversions and cumulative dose is defined in Appendix 18.8.

The following endpoints will be described for statistical analysis:

- Clinically meaningful reduction in CS dose from Baseline, defined by:
 - A reduction of daily prednisone-equivalent CS dose $\geq 25\%$ to a dose of ≤ 7.5 mg/day by Week 40 + 1 day (i.e. Week 41) and sustained through Week 52

AND

- No new BILAG A organ domain scores and no more than one new BILAG B organ domain score during Weeks 40 + 1 day (i.e. Week 41) through 52.

Subjects withdrawing from treatment before Week 40 or with missing data at Week 40 will be considered as non-responders. The analysis will be performed on the mITT subjects whose CS dose is greater than or equal to 7.5 mg at baseline.

- Change from Baseline to Week 52 in prednisone-equivalent CS daily dose.

Summary statistics for absolute value, CFB and percent CFB by visit during treatment period in prednisone-equivalent CS daily dose will be provided.

- Reduction by visit, from Baseline to Week 52, in prednisone-equivalent CS daily dose of zero to < 25%, 25% to 50%, > 50%, or an increase.

The same table will be produced with the following categories of prednisone-equivalent CS daily dose at Week 52: ≤ 6 mg, > 6 - 7.5 mg, > 7.5 – 10 mg, > 10 – 20 mg, > 20 – 30 mg and > 30 mg. The proportions are based on the observed subjects as the denominator.

- Cumulative prednisone-equivalent CS dose from Baseline until completion of the Treatment Period (absolute value only) will be described using summary statistics.

Cumulative prednisone-equivalent CS dose will be compared between placebo arm and evobrutinib arms with a pairwise non-parametric Wilcoxon rank sum test.

[figure not shown]
All CS doses will be listed for each subject and flagged for any doses not taken into account in calculation of the scheduled-visit dose (e.g. dose taken between two scheduled visits or dose with missing information). Subjects non-compliant with protocol rules on CS usage will be listed based on protocol deviation data (i.e. all subjects with PD code = PDEV52e).

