 - For discontinuers, Duration = Last IMP dose date + 14 – baseline visit date + 1

- If one subject does not receive any CS between baseline and end of treatment period then his daily dose will be set to 0 mg and change from screening value will be equal to 0 mg.
- Prednisone-equivalent daily dose [mg] by visit:
 - The prednisone-equivalent daily dose at visit X is calculated only if visit X is performed during treatment period (date of visit X \leq last treatment intake + 14 days).
 - At a scheduled visit, prednisone-equivalent CS daily dose is equal to the dose the subject is on at the scheduled visit. If several CS are taken at the same scheduled visit then all CS doses should be added. If a prednisone-equivalent CS dose stopped/changed at the scheduled visit date (Week X visit date), then the prednisone-equivalent CS dose started before (Week X visit date - 1 day) will be considered as the CS daily dose for that visit.
 - CS dose taken between two scheduled visits will not be taken into account in calculation of the scheduled-visit dose.
 - For subjects who completed the treatment period, CS dose that started on or after end of treatment will be excluded from the calculation.
 - All comparisons will be done compared to CS dosing at baseline. CS dosing at baseline is defined at CS dose taken the day of baseline visit (day 1). If patient did not receive any CS at baseline then CS dose is set to 0 mg.
 - For defining CS sparing effect endpoint (i.e. sustained reduction by W41 to Week 52), the derivation of prednisone-equivalent CS daily dose will be repeated at Week 40 scheduled visit using a different rule. If a prednisone-equivalent CS dose stopped/changed at the Week 40 scheduled visit date (Week 40 visit date), then the prednisone-equivalent CS dose started after (Week 40 visit date + 1 day) will be considered as the CS daily dose for that visit. Sustained reduction by Week 41 will be then programmed by checking that CS reduction is maintained between this new post-Week 40 (=Week 41) visit and Week 52 visit (i.e. CS dose at Week 52 is less or equal than CS dose at Week 41). The associated conditions related to CS sustained reduction (i.e. CS dose \leq 7.5 mg/day and \leq Day 1 CS dose, CS dose reduction from baseline \geq 25% and CS dose \leq 7.5 mg/day) will be checked for Week 41, 44, 48 and 52 visits.

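### Appendix 18.8.1.4 adds a Week 52 versus Week 41 dose test to sustained steroid reduction that Section 14.3.1 does not require, so the same dose record can be scored both ways

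*SAP*

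**What the plan says.** **Section 14.3.1 (SRI-4 in all subjects, SRI-6 in the HDA subgroup and SRI-4 in the serologically active subgroup, each with sustained OCS reduction).** The dose must be at most 7.5 mg/day and at most the Day 1 dose from Week 41 through Week 52. The section then says what is enough: "If the condition is met for all days during this period, the subject will be considered as having a sustained reduction of OCS Dose". It refers to Appendix 18.8 for calculating the daily dose: "Day 1 dose during Week 41 Through Week 52, the daily dose of CS will be calculated for each analysis visit from Week 41" onward.

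**Section 14.3.5 (clinically meaningful reduction).** The dose must fall by at least 25%, to at most 7.5 mg/day, "by Week 40 + 1 day (i.e. Week 41) and sustained through Week 52", and a BILAG condition must also hold. The section does not define what sustained means. The population is restricted: "The analysis will be performed on the mITT subjects whose CS dose is greater than or equal to 7.5 mg at baseline".

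**Appendix 18.8.1.4.** Sustained reduction is programmed as the reduction being maintained between the post-Week 40 value (labelled Week 41) and Week 52, explained as "CS dose at Week 52 is less or equal than CS dose at Week 41". The next sentence takes the dose limits of both endpoint types as associated conditions that "will be checked for Week 41, 44, 48 and 52 visits". A little earlier, the same list says: "All comparisons will be done compared to CS dosing at baseline".

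**The concern.** Section 14.3.1 gives a sufficient rule, and the appendix adds a requirement to it. A programmer who follows the section and one who follows the appendix would produce different responder flags from the same steroid records.

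The added test also does not measure stability. It compares only the first and last points of the window, so a rise in between that has reversed by Week 52 goes unseen, while a rise still present at Week 52 counts as failure even when every dose is within the limits.

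At stake are the responder counts, and the odds ratios built on them, for the three SRI/OCS endpoints, and the responder proportion for clinically meaningful reduction.

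**Working it through.** The SAP states no figure on this point, so there is none to reproduce. The check is to score illustrative dose records under each rule. The doses are examples only, not proposals.

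**Rules**, with b the Day 1 dose and d41, d44, d48, d52 the doses at the four checked points:

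- S (SRI/OCS limits, Section 14.3.1): every d ≤ 7.5 and every d ≤ b.
- C (dose part of clinically meaningful reduction, Section 14.3.5): b ≥ 7.5, every d ≤ 7.5 and every d ≤ 0.75 × b. This reads sustained as the limits holding throughout the window.
- X (comparison added in Appendix 18.8.1.4): d52 ≤ d41.

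The sections score by S or C. The appendix scores by S and X, or by C and X.

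| Record | Day 1 (mg) | Weeks 41, 44, 48, 52 (mg) | S | C | X | Appendix result |
|---|---|---|---|---|---|---|
| 1 | 20 | 5, 7.5, 7.5, 7.5 | met | met | not met | fail |
| 2 | 10 | 0, 0, 0, 2.5 | met | met | not met | fail |
| 3 | 20 | 7.5, 7.5, 7.5, 7.5 | met | met | met | pass |
| 4 | 20 | 5, 7.5, 7.5, 5 | met | met | met | pass |
| 5 | 5 | 2.5, 2.5, 5, 5 | met | outside population | not met | fail (SRI/OCS only) |

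**Record 1.** The highest dose is 7.5 mg, which is within 7.5 mg/day and below 20 mg. The smallest reduction from Day 1 is (20 − 7.5)/20 = 62.5%, above 25%. All limits hold, but 7.5 > 5, so X fails.

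**Record 2.** The smallest reduction is (10 − 2.5)/10 = 75%. All limits hold, but 2.5 > 0, so X fails.

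**Records 1 and 3.** Record 3 is never on a lower dose than Record 1 at any of the four points, yet Record 3 passes and Record 1 fails.

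**Records 1 and 4.** Both rise from 5 to 7.5 mg after Week 41. Record 4 passes because its dose is back at 5 mg at Week 52.

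**Record 5.** This bears only on the SRI/OCS endpoints, because a Day 1 dose of 5 mg is outside the Section 14.3.5 population.

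**Is X a separate test?** Yes. S and C compare each dose with a fixed ceiling and with the Day 1 dose. Neither implies d52 ≤ d41, as Records 1 and 2 show. The appendix checks those limits in addition to X. X also uses Week 41 as its reference, although the same list of rules names baseline as the reference for all comparisons.

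These records concern the dose component only. SRI response, or the BILAG condition, must still be met for a subject to be a responder.

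**The case against.** The best defence is that the parenthesis explains what maintaining a reduction means, and that no increase from Week 41 to Week 52 is a possible, stricter meaning of sustained. For clinically meaningful reduction this largely stands. Section 14.3.5 does not define the word and sends general rules to Appendix 18.8, so the appendix can be read as filling a gap. A reader might infer that all four endpoints are contradicted equally; the text does not support that.

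For the three SRI/OCS endpoints the defence fails. Section 14.3.1 already states what is sufficient and uses the appendix for dose calculation, not for a new criterion.

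Further limits are fair:

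- A reader might take a share of affected subjects from counting dose pairs. On a grid of four doses at Week 41 and Week 52, 6 of 16 pairs have the later dose higher. Any four ordered values give that count, and it says nothing about patients.
- A reader might infer that the arm that tapers furthest loses most. The SAP has no data on dose rises by arm.
- A reader might call the rise after Week 41 permitted. The rules on corticosteroid use are in the protocol, which is not at hand. All that can be said is that the rise stays within the endpoint's limits.
- The endpoints are non-confirmatory. Section 14.3 treats p-values for other secondary endpoints as nominal, and Section 14.3.5 names no inferential method for clinically meaningful reduction.

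**Conclusion.** The concern holds. For the three SRI/OCS endpoints, Section 14.3.1 and Appendix 18.8.1.4 contradict each other: a subject within both dose limits from Week 41 to Week 52, with a higher dose at Week 52 than at Week 41, meets the OCS component under one and fails it under the other. For clinically meaningful reduction, the appendix adds a condition that Section 14.3.5 does not state. This is a gap to close rather than a plain contradiction.

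Only subjects within the limits whose Week 52 dose exceeds their Week 41 dose are affected; for others who meet the limits at the four checked points the comparison changes nothing. How many there are, and how they fall across arms, cannot be computed from the SAP. Because X is an extra condition, removing it can only leave each arm's responder count unchanged or raise it. The effect on differences between arms is unknown.

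The two primary endpoints, the key secondary endpoints and the hierarchical testing in Section 14.1.2.4 are not touched. The conclusion rests on reading the parenthesis as a programmed condition, which its wording and the separate limit checks support.

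**What to change.** Reconcile Sections 14.3.1 and 14.3.5 with Appendix 18.8.1.4 so that the derivation matches the stated endpoint definition:

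- Remove the Week 52 versus Week 41 comparison from the derivation of the three SRI/OCS endpoints, leaving the limits in Section 14.3.1 as the rule.
- State in Section 14.3.5 whether the comparison applies to clinically meaningful reduction.
- While editing, settle whether the limits apply on all days, as in Section 14.3.1, or at the four checked points, as in the appendix.
- If the sponsor did intend the comparison for the SRI/OCS endpoints, it must appear in Section 14.3.1, and in Section 7 if it departs from the protocol. Section 7 lists no such change now.

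SAP version 4.0 follows review of the primary analysis results (Sections 6.3 and 6.4). The change should therefore be recorded as a documented correction, and responder counts by arm should be reported with and without the comparison.

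The text and code edits are small. The real cost is a rerun of the affected outputs and a disclosed correction made after unblinding.

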18.9 SAS Sample Code

This Appendix details how the statistical methods will be implemented with SAS software application.

18.9.1 SRI Response

Logistic regression: PROC LOGISTIC with SAS

The logistic regression can be implemented using the following SAS code:

```
proc logistic data=<dataset> descending;
  class TreatmentGroup(ref='Placebo') Region Race SLEDAI_2K_screening;
  model AVALC(event="Y") = TreatmentGroup Region Race
                        SLEDAI_2K_screening / orpvalue clodds=wald;
  ods output CLoddsWald=CLoddsWald;
run;
```

For primary analysis of the 2-primary endpoints and key secondary endpoint *SRI-4 response at Week 52 among serologically active subgroup*, output the 1-sided p-value ($\alpha=0.025$) as below:

- When the OR favors the active treatment (i.e. $OR > 1$), one-sided p-value = two-sided p-value / 2
- When the OR does not favor the active treatment (i.e. $OR \leq 1$), one-sided p-value = 1 – (two-sided p-value / 2)

The interaction can be implemented using the “*” symbol. For example, the following statement takes into consideration the interaction between treatment and region:

```
proc logistic data=<dataset> descending;
  class TreatmentGroup(ref='Placebo') Region Race SLEDAI_2K_screening;
  model AVALC(event="Y") = TreatmentGroup Region Race SLEDAI_2K_screening
                        TreatmentGroup * Region / orpvalue clodds=wald;
  ods output ParameterEstimates=ParameterEstimates CLoddsWald=CLoddsWald;
run;
```

Linear trend in log odds of SRI response for two-primary and key secondary endpoints: PROC LOGISTIC with SAS

In addition to the standard logistic model, the linear trend test can be implemented using the ESTIMATE and CONTRAST statements:

```
proc logistic data=<dataset>;
  class TreatmentGroup Region Race SLEDAI_2K_screening / param=glm;
  model AVALC(event="Y") = TreatmentGroup Region Race
                        SLEDAI_2K_screening;
  ESTIMATE "SRI response rate trend linear in treatment" TreatmentGroup 3 1 -1 -
3;
  CONTRAST "SRI response rate trend linear in treatment" TreatmentGroup 3 1 -1 -3
/ e;
  ods output
  Estimates=Estimates ContrastTest=ContrastTest;
run;
```

Logistic regression subgroup analysis: PROC GLIMMIX with SAS

In addition to the standard logistic model, the subgroup analysis can be implemented using the following code:

```
proc glimmix data=<dataset>;
  class TreatmentGroup (ref='Placebo') SLEDAI_2K_screening;
  model AVALC(event="Y") = TreatmentGroup SLEDAI_2K_screening TreatmentGroup*
  SLEDAI_2K_screening / alpha=0.05 dist=binary;
  lsmeans TreatmentGroup* SLEDAI_2K_screening / slicediff= SLEDAI_2K_screening
  oddsratio ilink cl;
  ods output Glimmix.LSMeans.SliceDiffs;
run;
```

Adjusted P-value:

The 12 raw p-values generated (for the two-primary endpoints and two key secondary endpoints with 3 treatment comparisons with placebo) are adjusted based on the hierarchical procedure by applying the methodology described in Section 14.1.2.4 (and further explained in Appendix 18.15). SAS PROC IML presented in Maurer 2014 will be used to generate the final adjusted p-values (i.e. adjusted for multiplicity).

MI process – MAR pattern: PROC MI with SAS

The following SAS code can be used to implement the MI with MAR pattern. The order of the SRI components must follow the one defined in the Section 14.1.2.4.

```
/******
STEP 1 : creation of monotone missing data structure
******/

/** _burn-in_NBITER_ will have to be adjusted by a convergence plot,
if convergence is not yet diagnosed after 200 iterations ***/
title "Step 1 : Create monotone structure" ;
proc MI data=<Dataset> out=outMAR1 seed=&seed. nimpute=&nimpute. noprint;
  var
  TreatmentGroup
  black (0=non-black 1=black)
  SLEDAI_2K_screening
  US (0=not US 1=US region)
  West (0=not Western Europe, 1=Western Europe region)
  Jap (0=not Japan region, 1=Japan region)
  SRIComp1_base SRIComp3_base
  SRIComp1_Day14 SRIComp2_Day14 SRIComp3_Day14

  /* continue to the last endpoint */

  ;
  mcmc chain=single initial=EM nbITER=200 NITER=100 impute=monotone ;
  EM MAXITER = 5000 ;
run ;

/******
```

```
STEP 2 : Apply multiple imputation
*****/
title "Step 2 : Apply MI procedure (MAR pattern)" ;
proc mi data=outMAR1 nimpute=1 seed=&seed. out=outMAR2 noprint;
  by _Imputation_;
  class TreatmentGroup race region SLEDAI_2K_screening;
  var
    TreatmentGroup race region SLEDAI_2K_screening
    SRIComp1change_Day14 SRIComp2_Day14 SRIComp3_Day14

  /* continue to the last endpoint */

;
  monotone regression;
run;
```

Then after applying the needed derivation of SRI score and the logistic analysis of interest for SRI-4, the next step consists in:

```
*****
STEP 4a : Pooling ODDS RATIOS and CI using Log Transformation
*****/
*** Log-transform odds ratio estimates and obtain standard error from confidence
intervals ***;
DATA lgsodds_t;
  SET lgsodds (WHERE=(INDEX(EFFECT,"TRT")));
  log_or_lr_value=LOG(ODDSRATIOEST);
  qn=quantile('NORMAL',.975);
  log_or_lr_se=(LOG(UPPERCL)-LOG(LOWERCL))/(2*qn);
RUN;
*** Combine transformed estimates;
PROC MIANALYZE DATA=lgsodds_t;
  MODELEFFECTS log_or_lr_value;
  STDERR log_or_lr_se;
  ODS OUTPUT PARAMETERESTIMATES=mian_lgsodds_t;
QUIT;
*** Back-transform combined values;
DATA mian_lgsodds_bt;
  SET mian_lgsodds_t;
  estimate_back = EXP(ESTIMATE); *Pooled odds ratio;
  qn=quantile('NORMAL',.975);
  LCL_back=Estimate_back*EXP(-qn*STDERR); *Pooled lower limit;
  UCL_back=Estimate_back*EXP(+qn*STDERR); *Pooled upper limit;
RUN;

/*****
STEP 4b : Pooling p-value
*****/
PROC MIANLYZE PARMs (CLASSVAR=CLASSVAL)=ParameterEstimatesMI
  CLASS TreatmentGroup;
  MODELEFFECTS TreatmentGroup;
  ODS OUTPUT PARAMETERESTIMATES=mian_logres
QUIT;
```

Then Step 4a and 4b are to be repeated for the analysis of SRI-6.

Pooling binomial proportion in each treatment arm after MI

```
*** Estimate proportions of responders in each treatment arm;
PROC FREQ DATA=datain_mi;
  TABLES resp / cl binomial(level=2);
```

```
Exact binomial;
BY _Imputation_ TreatmentGroup;
ODS OUTPUT BINOMIALPROP=prop;
RUN;
*** From ODS output dataset BINOMIALPROP, create a dataset
containing estimated proportion of responders in each
treatment arm and their standard errors;
DATA prop_trt;
MERGE
prop(WHERE=(Label1="Proportion")
KEEP=_Imputation_ TreatmentGroup nValue1 Label1
RENAME=(nValue1=prop))
prop(WHERE=(Label1="95% Lower Conf Limit")
RENAME=(nValue1=LOWERCL)
prop(WHERE=(Label1="95% Upper Conf Limit")
RENAME=(nValue1=UPPERCL)
qn = Quantile('NORMAL',.975)
prop_se = (UPPERCL - LOWERCL) / (2 * qn)
BY _Imputation_ TreatmentGroup;
RUN;
*** Combine proportion estimates;
PROC SORT DATA=prop_trt; BY TreatmentGroup _Imputation_; RUN;
PROC MIANALYZE DATA=prop_trt;
MODELEFFECTS prop;
STDERR prop_se;
BY TreatmentGroup;
ODS OUTPUT PARAMETERESTIMATES=mian_prop_trt;
RUN;
```

Tipping point sensitivity analysis

*1- Start by computing the number of missing response in each treatment at the willing visit in macrovariables: nmisspbo nmissd1 nmissd2 nmissd3.

*2- Then complete the tipping point analysis:

```
***TIPPING POINT ANALYSIS FOR BINARY DATA;
data resptip
  set resp;
  if TreatmentGroup='Pbo' then trtn=1;
  else if TreatmentGroup='Dose 1' then trtn=2;
  else if TreatmentGroup='Dose 2' then trtn=3;
  else if TreatmentGroup='Dose 3' then trtn=4;
  randnum=ranuni(200527);
  misspbo=&nmisspbo;
  missd1=&nmissd1;
  missd2=&nmissd2;
  missd3=&nmissd3;
run;
***Sort by random number allow cumulative imputation of failure /
success to subjects in random order;
PROC SORT data=resptip; BY randnum; QUIT;
DATA resptip2
  SET resptip;
  WHERE trtn in (1 2 3 4);
  ARRAY randcount(4);
  ARRAY t(4);
  *Each missing data will be identified by its number starting from 1, by each
treatment;
  RETAIN randcount 0;
```

```
newresp=resp;
IF resp=. THEN randcount(trtn)+1;
*Output misspbo*missd1 + misspbo*missd2 + misspbo*missd3 scenarios, ie all possible
combination of pbo with the dose;
DO t1=1 to misspbo
  DO t2=1 TO missd1;
  DO t3=1 TO missd2;
  DO t4=1 TO missd3;
  IF resp=. THEN DO;
    IF randcount(trtn)<=t(trtn) THEN newresp=1;
    ELSE newresp=0;
    OUTPUT;
  END;
  ELSE OUTPUT;
END;
END;
END;
END;
```

*3- Then apply primary analysis to the new dataset according to each tipping point scenarios (ie by t1 t2 t3 t4).

From that we could plot p-value of each dose versus pbo.

Looking at t1 vs t2 for the p-value of dose 1.

Looking at t1 vs t3 for the p-value of dose 2.

Looking at t1 vs t4 for the p-value of dose 4.

*Label variable in result dataset that will be displayed in plot;

```
data p;
set pvalue;
label pvalue="P-value"
  t1='N of responders among missing - Placebo'
  t2='N of responders among missing - Dose 1;
  t3='N of responders among missing - Dose 2;
  t4='N of responders among missing - Dose 3;
run;
*Select scenarios and treatment to plot;
%macro selscenartrt (scenarios=, trtnum=,out=)
  data &out.;
  set p;
  where bygroup in (&scenarios) and trtn in (&trtnum.)
%mend selscenartrt;
%selscenartrt (scenarios=%str("t1" "t2"), trtnum=%str(1 2),out=pt1t2)
%selscenartrt (scenarios=%str("t1" "t3"), trtnum=%str(1 3),out=pt1t3)
%selscenartrt (scenarios=%str("t1" "t4"), trtnum=%str(1 4),out=pt1t4)
```

*Plot the wanted comparison;

```
proc sort data=pt1t2;
  by t1 t2;
quit;
proc sgplot data=p;
  title1 "Adjusted p-value 1-side : Placebo vs Dose 1";
  heatmapparm x=t2 y=t1 colorresponse=pvalue / colormodel=TwoColorRamp discretex
discretex transparency=0.2 OUTLINE outlineattrs=(thickness=0.5pt color=gray);
  text x=j y=i text=nvalue2 / textattrs=(size=5pt) strip;
  gradlegend;
```

```
footnote1 justify=left "Placebo: N (ITTm) = xxx1, Observed Resp = xxresp1, Observed  
Non-Resp = xxnresp1 and Missing = &nmisspbo.";  
footnote2 justify=left "Dose 1: N (ITTm) = xxx2, Observed Resp = xxresp2,  
Observed Non-Resp = xxnresp2, Missing = &nmissd1.";  
run;
```

